1. SUMMARY

1.1. STUDY TITLE

MOLECULAR STUDY OF ORAL DYSBACTERIOSIS IN PEOPLE WITH OBESITY AND PREDIABETES OR DIABETES (SMILE)

1.3. CENTER WHERE THE TEST IS PLANNED TO BE CARRIED OUT

Hospital Regional Universitario de Malaga (Malaga).

1.4. RESEARCH ETHICS COMMITTEE THAT EVALUATED THE TRIAL

Investigación Provincial de Málaga Ethics Committee

1.5. MEDICATION/SUBSTANCE WITH WHICH THE TEST IS GOING TO BE CARRIED OUT

No medication or substance will be tested on patients, it is a descriptive observational study.

1.6. MAIN OBJECTIVE OF THE TRIAL

Investigate the possible differences in endocannabinoid levels and their correlation with inflammatory cytokines and microbial load in the oral cavity depending on the presence or absence of oral cavity disease in people with obesity and prediabetes or diabetes.

1.7. TRIAL DESIGN

Descriptive observational study.

1.8. ILLNESS OR DISORDER UNDER STUDY

- Prediabetes
- Diabetes mellitus type 2
- Obesity
- Oral dysbiosis
- Oral cavity disease (OCD)

1.9. MAIN AND SECONDARY VARIABLES

As MAIN VARIABLE, endocannabinoids in saliva and plasma (2-AG, AEA, PEA, OEA, DHEA, 2-LG, 2-OG; pmol/ml) will be studied .

And as SECONDARY VARIABLES are going to be studied:

- The bacteriological profile of the oral cavity (the following bacterial strains: *Aggregatibacter actinomycetemcomitans* , *Porphyromonas gingivalis* , *Tannerella forsythia* , *Treponema denticola* , *Prevotella intermedia* , *Fusobacterium nucleatum* , *Parvimonas micra* , *Campylobacter rectus* , *Eikenella corrodens* , *Veillonella kindergarden* and *Actinomyces naeslundii* for periodontal disease; and *streptococci mutans* , *S. sanguis* , *S. mitior* , *S. salivarius* and *S. milleri* for dental caries) ,
- The concentration of inflammatory cytokines in saliva and blood (interleukin [IL]-1 β , IL-6, IL-8, IL-10, IL-17, leptin, adiponectin, vascular endothelial growth factor [VEGF], Interferon [IFN]- γ and Tumor Necrosis Factor [TNF]- α),
- Glucose management (fasting blood glucose (mg/ dL), insulin (mUI/mL), HbA1c (%), HOMA-IR, HOMA2-IR, QUICKY, HOMA2%S, HOMA2%B) ,
- Adiposity and atherogenic profile [BMI (kg/m²)], waist circumference (cm), waist/hip ratio, waist/height ratio, blood pressure (mmHg), triglycerides (mg/dL),

- total cholesterol (mg/dL), HDL cholesterol (mg/dL), LDL cholesterol (mg/dL), total cholesterol/HDL, LDL/HDL and Triglycerides/HDL ratios ,
- Salivary parameters through sialometry (salivary flow), salivary viscosity, salivary pH and the impact profile on oral health (OHIP-14sp; WHO questionnaire) .

1.10. STUDY POPULATION AND TOTAL NUMBER OF PATIENTS

A total of 60 adult patients are expected to be included: 15 diagnosed with obesity and prediabetes with OCD, 15 diagnosed with obesity and prediabetes without OCD, 15 diagnosed with obesity and diabetes with OCD, and 15 diagnosed with obesity and diabetes without OCD.

1.11. TEST DURATION

Twelve months.

1.12. SCHEDULE AND EXPECTED COMPLETION DATE

- Study authorization date: Second quarter of 2023.
- Date of inclusion of the first patient: Fourth quarter of 2023.
- Date of inclusion of the last patient: Second quarter of 2024.
- Study closing date: Fourth quarter of 2024.

2. GENERAL INFORMATION

2.1. TEST IDENTIFICATION

Title and acronym :

MOLECULAR STUDY OF ORAL DYSBACTERIOSIS IN PEOPLE WITH OBESITY AND PREDIABETES OR DIABETES - **SMILE**

2.2. DESCRIPTION OF THE MEDICATION/SUBSTANCE UNDER STUDY

No medication or substance will be tested on patients, this is a descriptive observational study

2.3. DATA RELATING TO THE PROMOTER

Fundación Pública Andaluza para la Investigación de Málaga en Biomedicina y Salud (FIMABIS)

2.6. TEST DURATION

Twelve months.

3. RATIONAL BASIS OF THE ESSAY

3.1. INTRODUCTION

According to the International Diabetes Federation, 537 million adults (20-79 years) are living with **diabetes**, 1 in 10 people worldwide. This number is projected to rise to 643 million

by 2030 and 783 million by 2045¹. Type 2 diabetes (T2D) is the most common type of diabetes, accounting for more than 90% of all diabetes worldwide^{2,3}. It has been estimated that, in 2021, 541 million adults worldwide (10.6% of the total) had glucose intolerance and some 319 million adults (6.2% of the world's adult population), had altered basal glucose (ABG)¹, and it is estimated that by the year 2045, these figures will increase to 730 million adults (11.4%) and 441 million adults (6.9%), respectively¹.

Both glucose intolerance and ABG are conditions of elevated blood glucose levels above the normal range and below the diagnostic threshold for T2D, both situations being collectively called **prediabetes**. Prediabetes implies a greater risk of future development of T2D and the appearance of cardiovascular disease (CVD)³. It is estimated that the cumulative incidence of progression of T2D at five years after the diagnosis of glucose intolerance or GBA is 26% and 50%, respectively. T2D, in the absence of proper control, can cause damage to multiple organs and systems, leading to disabling and life-threatening health complications, such as CVD, nerve damage (neuropathy), kidney damage (nephropathy), amputation of lower limbs, vision loss and even blindness. Prediabetes and T2D are also important risk factors for **oral cavity diseases (OCD)**, with this risk being three times higher than among people without diabetes^{4,5}. Oral health depends on the maintenance of stable microbial communities, appearing oral disease occurs when pathogenic species exceed the normal flora⁶.

In the oral cavity, the presence of representative pathogenic bacteria is usually associated with two main diseases; *streptococcus mutans* and *Lactobacilli* with dental caries, and *Porphyromonas gingivalis*, *Fusobacterium nucleatum* and *Treponema denticola* with periodontal disease⁷. Gingivitis is a frequent form of inflammation of the gums, a step prior to periodontitis. ECHO are complications associated with T2D, being generally underestimated and underdiagnosed. Interestingly, there is evidence of a bidirectional relationship between the T2D condition and said oral conditions, with salivary levels of different pathogens correlated with blood glucose levels⁸⁻¹⁰. However, although inflammation seems to play a central role, the molecular mechanisms that link these pathological conditions are currently poorly understood.

The **endocannabinoid system (ECS)** is a lipid signaling machinery that regulates various biological processes within the body^{11,12}. Originally, it was composed of the lipid signaling molecules anandamide (AEA) and 2-arachidonoylglycerol (2-AG), two receptors, CB1 and CB2, and five enzymes responsible for the biosynthesis and degradation of these ligands: N - acyl phosphatidylethanolamine phospholipase D (NAPE-PD), diacylglycerol lipase alpha and beta (DAGL) for the synthesis of endocannabinoids, and fatty acid amide hydrolase (FAAH) and monoacylglycerol lipase (MAGL) for the catabolism of AEA and 2-AG, respectively¹³. This original conception of the SEC, however, has turned out to be too simplistic. Receptor heterodimers, non-canonical cannabinoid-sensitive receptors, and the ability of some ligands to act as receptor allosteric modulators have amplified this signaling system^{14,15} constituting what is now called **an endocannabinoidome**^{16,17}. It is now well known that the endocannabinoidome plays a key role in energy homeostasis and related diseases such as obesity, prediabetes, and T2D by acting on different organs, including the gut microbiota^{18,19}, and modulating key processes such as inflammation and oxidative stress.

For all these reasons, the present study aims to unravel the possible role of endocannabinoids and related lipids as mediators of OCD, which could help to develop new therapies based on this signaling system aimed at preventing and treating OCD in the context of prediabetes/T2D.

The association between T2D and periodontitis is bidirectional. Results from mechanistic studies indicate that T2D leads to a hyperinflammatory response in the periodontal microbiota and also affects inflammation resolution and repair, leading to accelerated periodontal destruction. On the other hand, it has been reported that periodontitis negatively affects glycemic control in patients with diabetes mellitus and contributes to the development of complications²⁰. Mechanistic links between periodontitis and T2D involve elevations in interleukin (IL)-1- β , tumor necrosis factor- α , IL-6, activator of nuclear factor receptor-kappa B ligand/ osteoprotegerin, oxidative stress, and expression Toll -Like Receptor (TLR)-2/4²¹. Therefore, inflammation is a central feature of the pathogenesis of diabetes and periodontitis.

However, the relationship between the oral microbiota and T2D is less explored. Several studies indicate that there are probably subtle differences in the microbial composition of the subgingival biofilm between people with and without T2D²², but the clinical relevance of this is not fully clear. Such differences may arise from the effect of T2D by altering the local environment within the periodontal pocket, in such a way that the growth of certain bacterial species is favored²³. Unfortunately, the specific mechanisms that exacerbate inflammation, oral microbiota dysbiosis, and periodontal disease in people with prediabetes and T2D are still unknown.

3.2. JUSTIFICATION

Diseases of the oral cavity are more frequent in people with prediabetes and diabetes, implying a decrease in the quality of life of these patients, adding to the multiple complications that these people develop during the progression of the disease. Precisely, one of the possible mechanisms that mediate the relationship between inflammation and oral dysbiosis in T2D is the endocannabinoidome. The novelty of this proposal consists precisely in studying the possible correlation between cannabinoids and related lipids, inflammatory markers and oral dysbiosis in people with prediabetes and T2D, determining the levels of these molecules in saliva and blood samples. To date, there are no studies that have addressed the analysis of these relationships, which may open the door to new ways to prevent and treat OCD in people with prediabetes and T2D.

3.3. HYPOTHESIS

For all of the above, our **hypothesis** is the following: **the endocannabinoidome has a similar role in the oral microbiota as in the intestinal one, so that its deregulation produces dysbiosis and an inflammatory state in the oral cavity, which may be linked to the OCD appearance.**

In fact, elevated levels of the cannabinoids AEA and 2-AG have been found in the saliva of obese people²⁴. Furthermore, ECS has been described in the oral cavity²⁵⁻²⁷ and several studies have demonstrated the presence and physiological relevance of the endocannabinoidome in the salivary glands^{25,28}.

3.4. AIMS

Based on this hypothesis, we propose the following main objective: **to study the possible differences in the levels of cannabinoids (2-AG, AEA, PEA, OEA, DHEA, 2-LG, 2-OG; pmol/ml), both in saliva and plasma, in a sample of patients with/without oral cavity disease, and with obesity and prediabetes, or with obesity and T2D.**

As secondary objectives will be studied:

- The bacteriological profile of the oral cavity (increase in the bacterial 16S rRNA amplicon, compared to the reference genes, for the following bacterial strains: *Aggregatibacter actinomycetemcomitans*, *Porphyromonas gingivalis*, *Tannerella forsythia*, *Treponema denticola*, *Prevotella intermedia*, *Fusobacterium nucleatum*, *Parvimonas micra*, *Campylobacter rectus*, *Eikenella corrodens*, *Veillonella kindergarten* and *Actinomyces naeslundii* for periodontal disease; and *streptococci mutans*, *S. sanguis*, *S. mitior*, *S. salivarius* and *S. milleri* for dental caries).

- Inflammatory cytokines in saliva and plasma (interleukin [IL]-1 β , IL-6, IL-8, IL-10, IL-17, leptin, adiponectin, vascular endothelial growth factor [VEGF], Interferon [IFN]- γ and Tumor Necrosis Factor [TNF]- α).

- Glucose management through fasting blood glucose levels (mg/dL), insulin (mUI/mL), HbA1c (%), HOMA-IR, HOMA2-IR, QUICKY, HOMA2%S, HOMA2%B.

- Adiposity and atherogenic profile, through BMI (kg/m²), waist circumference (cm), waist/hip ratio, waist/height ratio, blood pressure (mmHg), triglycerides (mg/dL), total cholesterol (mg/dL), HDL cholesterol (mg/dL), LDL cholesterol (mg/dL), total cholesterol/HDL, LDL/HDL, and Triglycerides/HDL ratios.

- Salivary parameters (sialometry (salivary flow), salivary viscosity, salivary pH and the impact profile on oral health (OHIP-14sp; WHO questionnaire)).

4. STUDY DESIGN

4.1. TYPE OF STUDY

Descriptive observational study.

A study with four groups is proposed: a group of obese diabetic subjects with a healthy mouth, a group of obese diabetic subjects with a diseased mouth, a group of obese pre-diabetic subjects with a healthy mouth, and a group of obese pre-diabetic subjects with sick mouth. All patients will be recruited on a voluntary and unpaid basis. After a meeting with each participant, where a detailed explanation about the study will be given, written informed consent will be obtained, as well as the necessary information to complete the medical evaluation questionnaire, which will allow determining their state of health and the criteria of inclusion and exclusion. Once the patient's eligibility is confirmed, they will be scheduled to fast for a saliva and blood extraction and an oral health questionnaire and/or an oral clinical examination.

The samples of the patients included in the study will be processed and frozen at -80°C until their subsequent analysis following standardized protocols. The samples will be stored in the biobank of the Hospital Regional de Málaga-IBIMA, which is part of the biobank of the public health system of Andalucía (BSSPA).

5. SUBJECT SELECTION

5.1. STUDY POPULATION

A population of patients of both sexes aged 40-65 years, with obesity and diagnosed with pre-diabetes, and with obesity and diabetes, and who meet the rest of the inclusion criteria, as well as who do not present any of the criteria, will be studied. of exclusion, and who agree to participate voluntarily in the study. For this, three studies led by our unit will be based on: The Pizarra study, an epidemiological study of the UGC of Endocrinología y Nutrición del Hospital Regional de Málaga that has provided detailed information on anthropometric, biochemical, eating habits and style parameters. of life in a cohort of about 1,700 subjects, the [contact] study, a national epidemiological study carried out on a sample of more than 5,000 people, coordinated by this Unit, and the April study, a nutritional intervention study on people with obesity and prediabetes. In addition, the databases of the obesity consultations of the UGC of Endocrinología y Nutrición del Hospital Regional de Málaga will be available. Based on these databases, we will proceed to contact the people who could meet the inclusion criteria, in order to arrange a recruitment visit for the study, following the guidelines of the Declaration of Helsinki (Fortaleza 2013) and the Standards of Good Clinical Practices. Personal data will be processed in accordance with REGULATION (EU) 2016/679 OF THE EUROPEAN PARLIAMENT AND OF THE COUNCIL of April 27, 2016 on the protection of natural persons with regard to the processing of personal data and the free movement of these dates; and Organic Law 3/2018, of December 5, Protection of Personal Data and guarantee of digital rights

5.2. SAMPLE SIZE

Based on previous publications that have reported the levels of endocannabinoids in saliva (20), at least 12 subjects are needed to detect as significant differences of 0.5pmol/ml of AEA and 25pmol/ml of 2-AG, which are the differences found between healthy people and obese people. It is intended to recruit 15 people with obesity, prediabetes and a healthy mouth, 15 people with obesity, prediabetes and a diseased mouth, 15 people with obesity, diabetes and a healthy mouth, and 15 people with obesity, diabetes and diseased mouth. To differentiate a healthy mouth from a diseased mouth, a complete oral evaluation will be carried out on all participants, which includes a review of the mucous membranes, an evaluation of the bacterial plaque and the presence of dental caries, and an evaluation of the health of the teeth, gums, including the depth of probing and the presence of gingival bleeding (see point 5.6).

5.3. INCLUSION CRITERIA

- Adults (40-65 years)
- With obesity and prediabetes: BMI 30-40 and HbA1c 5.7-6.4
- With obesity and diabetes: BMI 30-40 and previous diagnosis of diabetes

5.4. EXCLUSION CRITERIA

- Pregnant women
- Diagnosis of some type of neoplasia or treatment with radiotherapy and/or chemotherapy in the last year.
- Ongoing inflammatory diseases (Crohn's disease, ulcerative colitis, arthritis, etc.) and/or anti-inflammatory treatments
- Presence of systemic diseases of vital organs
- Participants in treatment with drugs that could alter salivary flow
- Smokers.
- Participants who have not followed the specifications prior to sampling
- Participants who did not sign the informed consent

5.5. ELIMINATION CRITERIA

- Inadequate amount of saliva to perform the tests

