5.7. SUBJECT IDENTIFICATION

Patients will be identified with a sequential numerical identification code, which will be assigned to each patient according to the correlative order of inclusion when they give their informed consent. In the event that a patient is included in the study and is considered unfit to continue in the study or the patient withdraws their consent, the code assigned to that patient cannot be reused for the next consecutively assigned patient.

The promoter will only be able to identify the subjects by the code that has been assigned to them, their date of birth, sex and date of signing the informed consent. The principal investigator will keep a record, protected by password, with the names of the patients and the assigned identification code.

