6.3. DEVELOPMENT OF THE TEST

Selection of patients and survey. Participants will attend the recruitment appointment after fasting for at least 8 hours. After verifying that they meet the inclusion and exclusion criteria and sign the informed consent, they will be given a survey that collects data on affiliation and lifestyle habits related to health and daily oral hygiene, including smoking and alcohol consumption; medical history that includes the medication taken, last visit to the dentist and risk factors and symptoms of oral disease, through questions that are easy to answer when self-identifying general symptoms compatible with gingivitis, periodontitis and dental caries (eg localized tooth sensitivity and in gums, bleeding gums, loose teeth, hypersensitivity in teeth to cold and/or heat, persistent bad breath, elongated teeth with receding and/or separated gums, modified bite, dry mouth, change of color in teeth, etc.).

Collection of salivary and blood samples. After completing the medical history, all patients will have their anthropometric data such as height, weight, waist circumference, hip circumference, systolic blood pressure, and diastolic blood pressure recorded. The research team dentist will perform a complete oral health diagnosis on the study subjects, using the World Health Organization (WHO) guidelines for diagnosing oral cavity disease ^{29,30}. Likewise, the oral health questionnaire will be passed. After the oral examination, **saliva** samples will be collected under resting conditions using the passive drooling method, in 15 mL tubes, every 1 min, for 5 min in the same tube. Together with the saliva samples, trained personnel will collect 9 ml of **blood samples**, under resting conditions, in EDTA tubes. The tubes will be centrifuged and the supernatant will be collected and stored at -80°C in the Biobank.

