7. STATISTIC ANALYSIS

7.1. COLLECTED VARIABLES

The following groups of variables are included in this essay:

- Anthropometric data: weight, height, body mass index, waist circumference, hip circumference, blood pressure.
- Clinical data: Previous or ongoing illnesses, current medication.
- Blood test data: Standard biochemistry (plasma glucose, insulin, plasma HbA1c, lipid profile, renal function, liver function, lymphocytes, hs-CRP, etc.), inflammatory markers (panel of inflammatory cytokines, including IL-6 , IL-1beta, and TNF-alpha), endocannabinoids (2-AG, AEA, PEA, OEA, DHEA, 2-LG, 2-OG).
- Saliva data: Salivary flow (to calculate unstimulated oral saliva flow), salivary viscosity, salivary pH, salivary protein concentration. Inflammatory markers (panel of inflammatory cytokines , including IL-6, IL-1beta and TNF-alpha), endocannabinoids (2-AG, AEA, PEA, OEA, DHEA, 2-LG, 2-OG), Bacteriological profiles. In addition, the oral health impact profile (OHIP-14sp) will be evaluated, both through the dental examination and through questions.

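### The elimination rule for too little saliva is not limited to the saliva assays; read naturally, it selects on salivary flow and discards usable plasma, flow and questionnaire data

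*Protocol*

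**What the plan says.** Section 5.5 of the protocol (Elimination criteria) consists of one line: "Inadequate amount of saliva to perform the tests". It follows the inclusion and exclusion criteria in section 5 (Subject selection). It gives no minimum volume, does not name the tests, and does not say what becomes of the participant's other data.

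The related passages are:

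- **Collection (6.3).** Resting saliva is collected by passive drool "every 1 min, for 5 min in the same tube". Blood is a separate draw at the same visit: "Together with the saliva samples, trained personnel will collect 9 ml of" blood from each participant.
- **Main variable (1.9).** "As MAIN VARIABLE, endocannabinoids in saliva and plasma", so plasma levels count as well as salivary ones.
- **Secondary variables (1.9, 7.1).** These include "Salivary parameters through sialometry (salivary flow), salivary viscosity, salivary pH" and OHIP-14sp. Section 7.1 lists "Salivary flow (to calculate unstimulated oral saliva flow" among the collected data.
- **Exclusions (5.4).** One criterion is "Participants in treatment with drugs that could alter salivary flow".
- **Participants who leave (5.7).** For a participant found unfit to continue, or who withdraws, "the code assigned to that patient cannot be reused for the next consecutively assigned patient". Nothing is said about replacing that person or keeping the data.

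**The concern.** Collection time is fixed, so the volume obtained is essentially the flow rate times five minutes. Too little saliva therefore mostly means flow below an unstated threshold, although incomplete collection or sample loss could also cause it. Removing such participants truncates a secondary variable at its low end, yet a very low volume is a valid flow result.

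The rule also reaches data that do not depend on saliva volume: plasma endocannabinoids and cytokines, blood biochemistry and OHIP-14sp. Complete saliva is needed to compare salivary levels and for the correlations with oral microbial load in the main objective (1.6). It is not needed to compare plasma levels between groups.

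Two things are at stake. If flow differs between participants with and without oral cavity disease (OCD), losses are unequal and the flow comparison is attenuated. If eliminated participants are not replaced, the plasma comparisons lose people with valid plasma. Section 6.3 lists dry mouth among the survey symptoms of oral disease, but the protocol nowhere says that measured flow differs between the groups.

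**Working it through.** **Scope of the rule.** Sections 5.3 and 5.4 act on people, 5.5 follows them in the same section, and 5.7 provides for a participant who is included and then found unfit to continue. No passage confines 5.5 to assays or retains other data. Participant-level removal is the natural reading, but it is not stated.

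**Size.** The protocol has no figure of its own to reproduce here. Everything below is an illustration except the total of 60 (section 1.10).

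Assumptions:

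- Log flow is normal with SD 1, with mean 0 without OCD and −0.5 with OCD.
- The two halves are equal in size (30 and 30).
- A sharp cut *c* removes an overall fraction *p* of 2, 5, 10 or 20%, which is 1.2, 3, 6 or 12 of 60.

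Formulas, for a group with mean μ, a = c − μ and λ = φ(a)/[1 − Φ(a)]:

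- fraction removed = Φ(a)
- mean of those kept = μ + λ
- variance of those kept = 1 + aλ − λ²
- *c* solves ½Φ(c) + ½Φ(c + 0.5) = p

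Worked case, p = 5%: c = −1.946.

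- Losses are Φ(−1.946) = 2.6% without OCD and Φ(−1.446) = 7.4% with OCD.
- λ is 0.062 and 0.152, so the observed difference is 0.062 − (−0.5 + 0.152) = 0.410. The shrinkage is 1 − 0.410/0.5 = 18.0%.
- The two variances average about 0.816 (SD 0.904), so in observed SD units the difference is 0.410/0.904 = 0.454, a shrinkage of 9.3%.

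| Eliminated overall | Lost, OCD v non-OCD | Log-flow difference (true 0.50) | Shrinkage, log | In observed SD units | Shrinkage, SD units |
|---|---|---|---|---|---|
| 2% | 3.1 v 0.9% | 0.452 | 9.5% | 0.477 | 4.7% |
| 5% | 7.4 v 2.6% | 0.410 | 18.0% | 0.454 | 9.3% |
| 10% | 14.2 v 5.8% | 0.361 | 27.7% | 0.426 | 14.9% |
| 20% | 26.8 v 13.2% | 0.296 | 40.9% | 0.384 | 23.2% |

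**Sensitivity** (shrinkage at 2/5/10/20% eliminated):

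- Untransformed flow, using E[exp(sX) | X > c] = exp(sμ + s²/2)·P(Z > c − μ − s)/P(Z > c − μ): 5.6/11.1/17.8/27.6% at log-SD s = 0.4; 4.2/8.5/13.9/21.7% at 0.6; 3.2/6.5/10.5/16.4% at 0.8.
- Half of the eliminations unrelated to flow: 5.7/11.4/18.6/29.5% (log) and 2.7/5.7/9.6/16.0% (SD units).
- A true shift of 0.3 gives 10.1/18.6/28.4/41.4% (log); a shift of 0.8 gives 8.4/16.5/26.2/39.6%.
- A shift of 0 gives equal losses and no bias.

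**Plasma precision.** Without replacement the standard error rises by √(60/n) − 1. For n = 58.8, 57, 54 and 48 this is 1.0, 2.6, 5.4 and 11.8% (1.0, 2.6, 5.5 and 12.2% with the unequal losses in the table). With replacement the rise is zero, but 60/(1 − p) = 61.2, 63.2, 66.7 or 75.0 people must be recruited, that is about 62, 64, 67 or 75, and the selection on flow remains.

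**The case against.** The strongest reply is that the harm rests on a reading the text does not state. Section 5.5 does not say that plasma goes unassayed or that data already collected are deleted, and its reference to performing tests could be read as concerning saliva testing only. Which data enter which analysis is often settled in the SAP. The study is also built on linked saliva and blood measurements, so requiring an adequate saliva sample is a defensible complete-case choice.

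The bias is conditional as well. It needs a non-trivial elimination rate and a flow difference between groups, and the protocol gives neither. The definition of a diseased mouth in 5.6 mentions neither dry mouth nor flow, and 5.4 already excludes users of flow-altering drugs. In SD units the shift runs from 0.02 (0.50 to 0.477 at 2%) to 0.12 (0.50 to 0.384 at 20%). The standard error of a standardised difference with 30 v 30 is about √(1/30 + 1/30) = 0.26, so the shift is below sampling error throughout.

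Much of this stands: the scope is not explicit, the size is unknown, and it is probably small. What does not stand is that the point can be left to the SAP. The elimination rule is fixed in the protocol, and an SAP cannot recover results from participants removed before their samples are assayed. Nor does the complete-case argument cover the plasma comparison or flow itself, neither of which needs enough saliva for the assays.

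**Conclusion.** The concern holds as a low-priority design point, with medium confidence. On its natural reading, section 5.5 selects largely on a secondary variable and discards valid data, including part of the main variable.

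The attenuation arises only if flow differs between groups, and the loss of plasma precision only if eliminated participants are not replaced. The protocol settles neither point. The exclusion of users of flow-altering drugs may keep the elimination rate near the low end of the illustration. There about one participant is lost, plasma standard errors rise by about 1%, and the flow difference shrinks by roughly 5% in SD units. The larger figures require 10 to 20% elimination, for which the protocol gives no basis.

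**What to change.** Reword section 5.5 so that an insufficient volume sets to missing only the saliva assays that cannot be run. State that the participant stays in the study with measured flow (including very low values), plasma endocannabinoids and cytokines, OHIP-14sp and clinical data. Report the number of insufficient samples by group.

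The cost is one line of protocol text. Numbers will differ between saliva and plasma outcomes, and saliva–plasma correlations will use the subset with both. Selection on flow will remain in the saliva assays, including salivary endocannabinoids; the change makes it visible but does not remove it.
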